# 6.3 Subject Exclusion Criteria

- HER-2 positive esophagogastric cancer. Patients with unknown HER2 status are permitted.
- Patients receiving any concurrent anticancer therapy or investigational agents with the intention of treating esophagogastric cancer. Last prior therapy must have been completed at least 2 weeks (14 days) prior to starting Nintedanib.
- Concurrent radiotherapy is not permitted for disease progression on treatment on protocol. However, symptomatic treatment for pre-existing non-target lesions would be allowed with approval from the principal investigator.
- Prior treatment with VEGFR inhibitor.
- Brain metastases or leptomeningeal disease.
- History of arterial thromboembolic (arterial blood clot) or hemorrhagic event with the exception of patients with pulmonary embolism stable on an anticoagulation regimen.
- Patients with a cerebrovascular accident or transient ischemic attack within the past six months.

- Patients on warfarin for any reason.
- Patient with known pre-existing interstitial lung disease.
- History or presence of clinically relevant cardiovascular abnormalities such as uncontrolled hypertension, congestive heart failure, New York Heart Association (NYHA) functional classification of 3, unstable angina or poorly controlled arrhythmia. Myocardial infarction within 6 month prior to the study entry.
- Patients with history of proteinuria grade  $\geq 2$ .
- Women of childbearing potential (WOCBP), or men who are able to father a child, unwilling to use a medically acceptable method of contraception during the trial and for at least three months after the end of active therapy.
- Women who are pregnant or breast-feeding.
- Persistence of clinically relevant therapy related toxicity from previous chemotherapy and/or radiotherapy. This does not include hemoglobin or other hematologic or laboratory criteria, as long as eligibility criteria are met as outlined in 6.1.
- Other malignancies within the past 5 years other than non-melanoma superficial skin cancer or carcinoma in situ of the cervix.
- Concurrent medical conditions or injury which may increase the risk of toxicity, including ongoing or active infection, history of significant bleeding disorder unrelated to cancer (congenital bleeding disorders, acquired bleeding disorders within one year), history of HIV-positive, or active or chronic hepatitis C and/or B infection.
- Known or suspected active drug or alcohol abuse.
- Gastrointestinal disorders or abnormalities that would interfere with absorption of the study drug. Patients who are unable to orally swallow the study medication.
- Known hypersensitivity to trial drug.

# 7.0 RECRUITMENT PLAN

This will be a single institution, phase II study. Patient with metastatic or recurrent esophageal, gastric, and gastroesophageal (GE) junction cancer that are eligible will be identified for enrollment from MSKCC clinical practice and clinic lists. No additional measures, e.g. advertisement, payment to patients, will be employed to recruit patients. Patients will be accrued to this study without regard for gender or minority status.

#### Inclusion of women and minorities

The investigators take due notice of the NIH policy concerning inclusion of women and minorities in clinical research populations. There will be no limitations with regards to race or gender.

Our institutional demographics for accrual of patients on esophageal and GE junction cancer trials reflect the national incidence of this disease. 10-15% of our patients have been women. African-American males comprise 3-5% of patients treated on protocol. Given that our protocol accrual closely reflects the national incidence of this disease, no specific strategy will be undertaken to recruit women or persons of color on this trial.

This protocol does not include children because the number of children with esophageal, gastric and GE junction cancer is very small and because the majority are already accessed by a nation-wide pediatric cancer research network. This statement is based on exclusion 4b

of the NIH Policy and Guidelines on the Inclusion of Children as Participants in Research Involving Human Subjects.

# 8.1 PRETREATMENT EVALUATION

To be completed within 2 weeks of study entry:

- History and physical exam including vitals, height, weight, performance status.
- Evaluation of concomitant medications and toxicity assessment.
- Serum pregnancy test for women of childbearing potential (WOCP) In addition, all WOCP should be instructed to contact the Investigator immediately if they suspect they might be pregnant at any time during the study participation.
- Laboratory evaluation including a complete blood count, PT/PTT, comprehensive chemistry panel (includes BUN, creatinine, ALT, AST, albumin, glucose, total protein, calcium, bilirubin, bicarbonate, sodium, chloride, potassium, alkaline phosphatase).

To be completed within 4 weeks of study entry:

- Electrocardiogram
- CT scan or MRI documenting all measurable or evaluable disease. All measurable lesions used to define response must be >10mm in size. The primary tumor is excluded. Lesions within prior radiation fields are permitted as long as these lesions have documented progression in size.

To be completed any time prior to starting therapy:

- Histological confirmation of esophagogastric adenocarcinoma prior to study enrollment.
- Available tumor tissue (20 unstained slides or tumor block) will be submitted for future molecular analysis (SEE SECTION 10 "Correlative Studies") but not be required prior to registration. Note: if tissue is depleted, patient will still be eligible after discussion with the PI.

# 9.1 TREATMENT/INTERVENTION PLAN

# 9.2 Agent administration

Treatment will be administered on an outpatient basis. Nintedanib is supplied as 100mg and 150mg capsules. The starting dose of Nintedanib is 200mg orally twice daily for 28 days continuously, unless interrupted for intolerable toxicity. There is no planned interruption between treatment cycles unless clinically indicated. The cycle start date will coincide with the physician visit date. Because of the potential need for physician visit scheduling to vary (due to both physician and patient issues), to avoid violation of, and deviation from, the protocol, physician visits may vary by up to one to fourteen (1-14) days from a strict 28 day schedule.

Nintedanib will be taken on days 1-28 of each 28-day cycle. Patients will swallow the soft gel capsule whole with approximately 250 mL of water each morning and evening after eating. The capsule cannot be crushed or dissolved.

In case of misdosing, patients should proceed with the intake of medication according to the predefined schedule and take the next scheduled dose when it is due. Patients with emesis should not take a replacement dose. A study diary will be completed by patients to ensure compliance with Nintedanib (see Appendix I).

# **Concomitant Therapy**

The use of investigational or anticancer agents is not allowed while patients are on this study. However, symptomatic treatment of tumor associated symptoms is allowed; such as radiation therapy with palliative intent and symptom control, provided that radiation does not affect target lesions and the reason for radiation does not reflect progressive disease. Concomitant medication, or therapy to provide adequate supportive care, may be given as necessary. If concomitant therapy is clinically indicated, patients may temporarily discontinue Nintedanib therapy and resume treatment following consultation with the treating physician and Principal Investigator.

# 9.3 Dose delay/modification

Intrapatient dose reduction will be allowed depending on the type and severity of toxicity encountered provided that criteria for patient withdrawal from study treatment have not been met. The dose levels for Nintedanib are as described below:

Starting dose 0	Nintedanib 200mg twice daily
Dose level -1	Nintedanib 150mg twice daily
Dose level -2	Nintedanib 100mg twice daily

If further dose reduction is required, the patient should be taken off-protocol.

If the dose of Nintedanib is reduced due to toxicity, it will stay at the lower dose level for the entire time of administration on protocol.

Patients who require a treatment delay of ≥21 consecutive days should also be taken offprotocol.

# 9.4 Suggested Medical Management of Nintedanib associated toxicities

# 9.4.1 Management of diarrhea

diarrheal treatment	
	Nintedanib after recovery of diarrhea 
	diarrheal treatment

Grade 1	Continue Nintedanib	No dose reduction of Nintedanib
	No Anti-diarrheal treatment	
Grade 2	Continue Nintedanib	No dose reduction of Nintedanib
	Anti-diarrheal treatment according to	
	the local standard e.g. Loperamide p.r.n.	
	despite optimal medical management O	R
Grade > 3 OR Any diarrhea inde	pendent of CTCAE grade leading to hosp	italization of the patient
First episode	STOP Nintedanib until recovery 	Reduce Nintedanib dose to
	AND	150 mg BID after recovery of
	Anti-diarrheal treatment according to	diarrhea 
	the local standard e.g. Loperamide p.r.n	
Second episode	STOP Nintedanib until recovery 	Reduce Nintedanib dose to
	AND	100 mg BID after recovery of
	Anti-diarrheal treatment according to	diarrhea 
	the local standard e.g. Loperamide p.r.n.	
Third episode	PERMANENTLY discontinue	PERMANENTLY discontinue
	Nintedanib treatment	Nintedanib treatment
	AND	
	Anti-diarrhoeal treatment according to	
	the local standard e.g. Loperamide p.r.n.	

 Until resolution to less than or equal to the patient's pre-therapy status at study enrollment.

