# 9.4.3 Management of Nausea and Vomiting

In order to reduce the occurrence and the intensity of emesis the patients should be treated according to the following recommendations:

	Dose of Nintedanib				
No antiemetic treatment	No dose reduction				
No Nintedanib treatment pause	No dose reduction				
Antiemetic treatment according to local standard					
of care e.g., metoclopramide or					
prochlorperazine					
If ineffective, patients should be treated accor-					
ding to treatment of vomiting > 2 or nausea					
CTCAE Grade ≥ 3.					
	No Nintedanib treatment pause   Antiemetic treatment according to local standard of care e.g., metoclopramide or prochlorperazine   If ineffective, patients should be treated according to treatment of vomiting ≥2 or nausea				

Vomiting ≥2 and/ or Nausea ≥ 3		
First episode	Treatment with Nintedanib discontinued and resumed upon recovery  Antiemetic treatment according to local standard of care e.g.: with 5-HT 3 receptor antagonist* and/or corticosteroid	Nintedanib: dose reduction 
Second episode	Treatment with Nintedanib discontinued and resumed upon recovery  Treatment as above	Nintedanib: dose reduction 
Third episode	As above	Nintedanib discontinuation

CTCAE grade  $\leq$  1 or baseline at study enrollment.

Nintedanib dose reductions : from 200 mg bid to 150 mg bid and from 150 mg bid to 100 mg bid \* Note: Tropisetron and dolasetron should be avoided due to genetically polymorphic metabolism by CYP2D6.

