# 13.1 CRITERIA FOR REMOVAL FROM STUDY

If at any time, the patient develops progressive disease he/she will be taken off study and referred for alternative therapy. If at any time the patient develops unacceptable toxicity that fails to resolve after a maximum treatment delay of 4 weeks, he/she will be removed from study. Before being removed from the study, patients will be scanned to assess the response. If the off study scan shows progression of disease then the patient will be considered as a non-responder, while a CR or PR will be considered as response. A patient will be withdrawn from the study treatment in the following circumstances:

- Patient is no longer able to participate in the study (e.g. AE, surgery, concomitant diagnoses, concomitant therapies or administrative reasons); in such a case the Investigator's reason for patient's removal must be recorded in CRDB.
- Patient withdrawal of consents or election to discontinue participation in the trial.

- Significant deviation from the protocol or eligibility criteria; such patients will be considered protocol violations and removed from study.
- Non-compliance with study or follow-up procedures.
- Drug related AE(s) that have not resolved after 3 weeks of treatment interruption. Exception to this in patients who derive obvious clinical benefit according to the investigator's judgment could be considered upon discussion with Principal Investigator. The dose reduction scheme provided should be followed in this case.
- Repeat episodes of drug related toxicity despite dose reduction to Nintedanib 100mg twice daily dose.
- Documented progressive disease.
- Patients who become pregnant while on study.

As soon as a patient is withdrawn from the study treatment, the End of Treatment (EOT) visit has to be performed (not in case patient has withdrawn consent). Every effort should be made to follow-up patients in case an adverse event is still ongoing at the time of withdrawal.

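### Section 9.4.1 sets the restart dose after diarrhea by episode number, not current dose, so read literally a patient already at 150 mg BID restarts at 150 mg BID

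*Combined protocol and SAP*

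**What the plan says.** Section 9.3 defines three dose levels: 200, 150 and 100 mg BID. It is permissive about when to move between them: "Intrapatient dose reduction will be allowed depending on the type and severity of toxicity encountered". Two of its rules are firm. A dose reduced for toxicity is not raised again ("it will stay at the lower dose level for the entire time of administration on protocol"), and there is no level below 100 mg BID ("If further dose reduction is required, the patient should be taken off-protocol").

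Section 9.4, headed as suggested management, has three toxicity-specific parts.

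- **Diarrhea (9.4.1).** For a qualifying episode the drug stops until recovery. The first-episode row then gives the restart dose as "150 mg BID after recovery of" diarrhea and the second-episode row as "100 mg BID after recovery of" diarrhea. A third episode ends treatment. The only footnote defines recovery.
- **Liver enzymes (9.4.2).** Most of the table is not legible in the extracted text, but its footnote defines a reduction as one level down from the current dose.
- **Nausea and vomiting (9.4.3).** For "Vomiting ≥2 and/ or Nausea ≥ 3", the first and second episodes each lead to a reduction "from 200 mg bid to 150 mg bid and from 150 mg bid to 100 mg bid", and the third to discontinuation.

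Section 13.1 withdraws patients for, among other reasons, "Repeat episodes of drug related toxicity despite dose reduction to Nintedanib 100mg twice daily dose".

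**The concern.** The diarrhea rows suit a patient who starts at 200 mg BID and has only diarrhea. They do not say what to do for a patient already reduced for something else. Suppose such a patient is at 150 mg BID after vomiting and then has a first qualifying diarrhea episode. The row's verb asks for a reduction, but the number it prints is the dose on which the episode occurred.

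Two things are at stake. One is safety: a patient who has already shown poor tolerance may be restarted, after severe diarrhea, at an unchanged dose. The other is consistency: one physician may follow the printed number and another the verb, so the same history could be managed in two ways. Section 11.1 lists diarrhea, nausea, vomiting and AST/ALT elevation among the likely events at doses up to 200 mg BID, so a sequence of two different toxicities is plausible in this trial.

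**Working it through.** The plan states no figure on this point to reproduce. The check sets the printed rules against each possible current dose.

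**Inputs.** Dose levels 200, 150, 100 mg BID and no re-escalation (Section 9.3). Diarrhea restart dose: episode 1 = 150, episode 2 = 100, episode 3 = stop (Section 9.4.1). Vomiting step: 200 to 150, 150 to 100 (Section 9.4.3).

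**Step 1: change at restart = printed dose − current dose (mg per intake).**

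| Current dose | Diarrhea episode | Printed restart dose | Change | One-level step |
|---|---|---|---|---|
| 200 | first | 150 | 150 − 200 = −50 | 150 |
| 150 | first | 150 | 150 − 150 = 0 | 100 |
| 100 | first | 150 | 150 − 100 = +50 | none left |
| 150 | second | 100 | 100 − 150 = −50 | 100 |
| 100 | second | 100 | 100 − 100 = 0 | none left |

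A second episode at 200 mg BID does not arise, because the first has already lowered the dose and Section 9.3 keeps it there. The +50 is barred by the same rule.

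**Step 2: does order matter?** Take one vomiting episode of grade 2 or more (V) and one first qualifying diarrhea episode (D), with the rows read literally.

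- D then V: 200, 150, 100 mg BID. Final daily dose 2 × 100 = 200 mg.
- V then D: 200, 150, 150 mg BID. Final daily dose 2 × 150 = 300 mg.
- Ratio: 300 / 200 = 1.5, so the daily dose is 50% higher when vomiting comes first.

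**Step 3: does another section require the missing step at 150 mg BID?** Section 9.3 permits a further reduction but does not order one. The repeat-toxicity bullet of Section 13.1 covers only patients already reduced to 100 mg BID. No other text prescribes a dose for this case.

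**Step 4: the same paths with a one-level step from the current dose.**

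- D then V, and V then D: both 200, 150, 100.
- D, D (diarrhea only): 200, 150, 100, as now.
- V, D, D: printed rules give 200, 150, 150, 100. The one-level rule gives 200, 150, 100, then off protocol at the second diarrhea episode.

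**The case against.** The strongest reply is that no sensible physician would be misled. The row says to reduce, which cannot be obeyed by staying at 150 mg BID. The section is headed as suggested management, and Section 9.3 allows 100 mg BID with no deviation. This stands to the following extent: a reader might infer that the plan denies these patients a reduction, and the documents do not support that. The 200, 150, 150 path is one literal reading, not a required outcome. What remains is that the printed number and the verb disagree and nothing says which governs.

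A second reply is that other protections apply. This also stands. At any dose the drug stops until the diarrhea returns to pre-therapy status, anti-diarrheal treatment is given, and a delay of 21 days or more takes the patient off protocol. A second diarrhea episode leads to 100 mg BID and a third to permanent discontinuation. A reader might infer that Section 13.1 gives no cover above 100 mg BID, but that is true only of its repeat-toxicity bullet. Its rules on unresolved toxicity and on adverse events that prevent participation have no dose condition. None of these protections sets the restart dose after a first episode.

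A reader might also infer from the +50 in the table that a patient at 100 mg BID would be re-escalated. Section 9.3 rules that out.

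Finally, the 50% is a ratio of two dose levels and does not measure harm. Section 3.8.3 reports drug-related diarrhea in 47.9% and vomiting in 42.5% on nintedanib monotherapy in lung cancer, at 150 or 250 mg BID. Those are neither trigger-grade rates nor rates of both events in one patient, so they show only that both toxicities are common.

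**Conclusion.** The point holds as a minor safety and consistency correction. Section 9.4.1 ties the restart dose to the diarrhea episode number and ignores the current dose. Read literally, it leaves a patient already at 150 mg BID unchanged after a first qualifying episode, and the step to 100 mg BID is left to judgment.

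For the pair of toxicities worked through above, the size is a final dose of 300 rather than 200 mg/day, on the assumption that the physician follows the printed number. How many of the 32 patients would be affected cannot be derived, because the protocol gives neither trigger-grade rates nor co-occurrence. The trigger row is partly lost in the extracted text, so the list of qualifying episodes may be incomplete. The episode rows and the footnote are legible, and the conclusion rests on those.

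A reader might go on to infer an effect on the trial's statistical conclusion. Nothing in the documents supports that: the 10% and 28% design values, the 32 patients and the rule of 6 or more do not depend on this wording.

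**What to change.** In the first- and second-episode rows of Section 9.4.1, replace the fixed doses with: *reduce by one dose level from the current dose (200 to 150, or 150 to 100 mg BID); if already at 100 mg BID, discontinue and take the patient off protocol per Section 9.3*. Keep permanent discontinuation at the third episode. The 100 mg BID case should be spelled out. A first diarrhea episode at that dose, reached through another toxicity, is not clearly a repeat episode under Section 13.1, and Section 9.3 acts only if a further reduction is required.

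The cost is the wording of two table rows. Sections 9.3 and 13.1, the visits, the sample size and the analysis stay as they are, and patients with diarrhea alone are dosed exactly as now. The downside is that a few patients are reduced, or come off protocol, one episode earlier. Under Section 12.2, such a patient who then starts another therapy counts as a failure at that time.

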# 9.4.2 Management of Liver Enzyme Elevations

If liver enzyme elevations are considered to be related to Nintedanib, the following algorithm should be followed. This recommendation for the management of Nintedanib - induced liver toxicity is valid ONLY for patients with inclusion criteria: AST/ALT < 1.5 ULN and bilirubin ULN in patients with no metastases in liver and, AST/ALT < 2.5 ULN and bilirubin  $\leq$  ULN in patients with metastases in liver.

ALT, AST and bilirubin elevation	1st episode	2nd episode	3rd episode
ALT and/or AST ≤ 5x ULN with bilirubin ≤ 1.5 ULN	Continue Nintedanib, No dose reduction	Continue Nintedanib, No dose reduction	Continue Nintedanib, No dose reduction

\*CTCAE grade  $\leq$  1 or baseline at study enrollment.

Nintedanib dose reductions : from 200 mg bid to 150 mg bid and from 150 mg bid to 100 mg bid

CTCAE grades for AST/ALT (version 3.0): Grade 1 means ALT or AST = ULN- 2.5 x ULN Grade 2 means ALT or AST > 2.5-5.0 x ULN Grade 3 means ALT or AST > 5-20.0x x ULN Grade 4 means ALT or AST > 20.0 x ULN

CTCAE grades for bilirubin (version 3.0): Grade 1 means > ULN- 1.5 ULN Grade 2 means > 1.5 ULN - 3x ULN Grade 3 means > 3x ULN - 10 ULN Grade 4 means >  $10 \times ULN$ 

# 9.4.3 Management of Nausea and Vomiting

In order to reduce the occurrence and the intensity of emesis the patients should be treated according to the following recommendations:

	Dose of Nintedanib				
No antiemetic treatment	No dose reduction				
No Nintedanib treatment pause	No dose reduction				
Antiemetic treatment according to local standard					
of care e.g., metoclopramide or					
prochlorperazine					
If ineffective, patients should be treated accor-					
ding to treatment of vomiting > 2 or nausea					
CTCAE Grade ≥ 3.					
	No Nintedanib treatment pause   Antiemetic treatment according to local standard of care e.g., metoclopramide or prochlorperazine   If ineffective, patients should be treated according to treatment of vomiting ≥2 or nausea				

Vomiting ≥2 and/ or Nausea ≥ 3		
First episode	Treatment with Nintedanib discontinued and resumed upon recovery  Antiemetic treatment according to local standard of care e.g.: with 5-HT 3 receptor antagonist* and/or corticosteroid	Nintedanib: dose reduction 
Second episode	Treatment with Nintedanib discontinued and resumed upon recovery  Treatment as above	Nintedanib: dose reduction 
Third episode	As above	Nintedanib discontinuation

CTCAE grade  $\leq$  1 or baseline at study enrollment.

Nintedanib dose reductions : from 200 mg bid to 150 mg bid and from 150 mg bid to 100 mg bid \* Note: Tropisetron and dolasetron should be avoided due to genetically polymorphic metabolism by CYP2D6.

